1 PURPOSE OF THE STUDY

The purpose of this clinical study is to evaluate the safety and efficacy of bleomycin-based electrochemotherapy (ECT) in treating primary liver tumours in a phase I and II clinical study.

This will be achieved by:

- applying treatment in a controlled manner based on pre-clinical and clinical experience obtained in the ESOPE project;
- evaluating the procedures and results achieved;
- preparing standardized procedures;
- disseminating these new approaches to treatment using written and audio-visual materials, as well as by attending and organizing expert meetings.

The study is designed as an institutional study (at the University Medical Centre Ljubljana) conducted in cooperation with the Institute of Oncology Ljubljana and the Faculty of Electrical Engineering (University of Ljubljana), as well as an industrial partner, IGEA s.r.l., Carpi, Italy, which will provide technical support for the study. In phase I, 10 patients will be included in the study, and in phase II (i.e. the extension of the study), an additional 15 patients who meet the inclusion criteria will be included.

The study will be carried out within the P3-0003 “Razvoj in ovrednotenje novih terapij za zdravljenje malignih tumorjev” (Development and Evaluation of New Therapies for Treating Malignant Tumours) research programme headed by [name], PhD.

Principal investigators:

[name], MD (surgeon)
Assist. [name], MD, PhD (surgeon)

Study coordinators:

[name], PhD (researcher)
[name] [name], PhD (gastroenterologist)

Coordinators of the clinical part of the study:

Head physician [name] (surgeon)
Assist. [name], (surgeon)

Colleagues:

University Medical Centre Ljubljana

[name] (gastroenterologist)
[name] (radiologist)
[name] (surgeon)
Assist. [name] (surgeon)
Assist. [name], PhD (surgeon)
Head physician [name] (cardiologist)

Institute of Oncology Ljubljana

[name], PhD (surgeon)
Assist. [name] (surgeon)
[name] (surgeon)
[name] (research nurse)

[name] [name], PhD (researcher)

Faculty of Electrical Engineering, University of Ljubljana

[name], PhD (researcher)

[name], PhD (researcher)

[name] (researcher)

[name] (researcher)

[name] (researcher)

[name] (researcher)

2 STARTING POINTS

The Principles of Electroporation and Electrochemotherapy (ECT)

By exposing a cell to an external electric field, a transmembrane voltage is established on the cell membrane. When the threshold value is exceeded, this voltage causes electroporation of the cell membrane, i.e. the formation of hydrophilic pores, which allow the increased passage of molecules into the cell.¹

The principle of electrochemotherapy (ECT) is based on exposing the tumour to pulses of electroporation delivered by specific electrodes. This allows the passage of previously applied hydrophilic cytostatics, e.g. bleomycin and cisplatin, into the cells.² Because the intake of cytostatics is only increased in the areas exposed to the electroporation pulses, ECT is a local treatment method. In addition to the direct action of cytostatics on tumour cells, ECT has an indirect vascular-disrupting effect, because cytostatics act on the endothelial cells in the tumour vasculature.³ The doses of cytostatics used in ECT are extremely low, resulting in minimal or no systemic toxicity.⁴ Furthermore, the application of electroporation pulses reduces the blood flow in the tumour, which keeps the cytostatics in the tumour for a longer period, thus making the treatment more effective.³

Clinical Applications of ECT

In the early 1990s, the team at the Institute of Oncology Ljubljana headed by [name], PhD, played an active part in pioneering clinical studies on treating cutaneous and subcutaneous tumours with ECT.⁵ According to the findings of these first clinical trials, an 80% objective response of the treated tumour nodules is achieved using ECT.⁶ Our team also helped draw up and publish standard surgical procedures for treating cutaneous and subcutaneous tumours using ECT. Today, ECT is a well-established method for treating malignant melanoma metastases, especially as part of palliative care,

in 15 European countries. In 2012, 2500 patients were treated with ECT and, according to several databases, ECT is now used in 135 oncology centres.

The first recorded clinical case of treating a deep-seated tumour with ECT involved treating melanoma metastases in thigh muscles.⁷ Experience in treating other types of soft tissue tumours with ECT is good but limited to a few clinical cases and studies involving a small number of patients.⁸⁻¹¹ In addition to treating deep-seated soft tissue tumours, ECT is used to treat deep-seated tumours in the internal organs. Brain and liver metastases have already been shown to be effective targets of ECT.¹²⁻¹⁴ The results of a clinical study on electrochemotherapy used to treat liver metastases of stage I and II colorectal cancer prove the safety and efficacy of this approach. Preliminary results have already been published for the case of one patient, where the treatment procedure is described in detail.¹⁴ Conclusions on safety and efficacy are in the process of publication for the first 17 patients treated with electrochemotherapy. No serious side effects attributable to ECT were observed in the study, and the efficacy results suggest an 80% response from the treated metastases to ECT, which is comparable to that of skin metastases.

Treatment of Primary Malignant Liver Tumours

Primary malignant liver tumours (carcinomas) represent a larger group of tumours that originate from various liver cells. Among such tumours, hepatocellular carcinoma (90%) and intrahepatic cholangiocarcinoma (8.5%) are the most common, while other primary liver carcinomas are significantly rarer. Liver tumours are the sixth most common cancer in the world and represent the third most common cause of death from cancer. The incidence of liver tumours is increasing worldwide, including in Slovenia, where the incidence is 9.3 in men and 4.6 in women per 100,000 people per year. The current treatment strategy is based on the resection of the affected liver parenchyma or radiofrequency ablation – these being the two methods of definitive treatment or bridging therapy to possible liver transplantation. Depending on the stage of the disease, transarterial chemoembolization (TACE), hepatic intra-arterial injection of lipiodol and systemic therapy with sorafenib are also considered palliative treatments. Radical liver resection or liver transplantation are the only promising treatment methods with a 5-year survival rate that can be greater than 50%. Radiofrequency ablation (RFA) can be used as a definitive treatment method (it can be repeated) or as bridging therapy to possible life-saving liver transplantation. RFA and percutaneous ethanol-lipiodol injection are suitable for smaller tumours and for tumours in specific locations (the proximity of blood vessels, subcapsular location). RFA is also offered to patients with individual smaller metastases as a

local form of treatment. Tumours that grow into the inferior vena cava or into the area of the large hepatic and portal veins, or on which RFA has little or no effect due to cooling, are particularly problematic. Therefore, new and more effective approaches to treating liver metastases are being sought for such patients. Distant cancer is usually treated with systemic chemotherapy or biological drugs, which are only partially successful while producing high systemic toxicity.

At the University Medical Centre Ljubljana, in cooperation with the Institute of Oncology Ljubljana, a phase I (10 patients) / II clinical study will be designed to assess the safety and efficacy of treatment for primary liver tumours using ECT. We aim to include an additional fifteen (15) patients within phase II using this protocol. The study aims to prove that treating primary liver tumours using ECT is a safe method even in hard-to-reach locations. Using imaging, we will also assess the response to therapy and the asymptomatic interval.

Planning ECT Treatment

The ECT treatment of deep-seated tumours in internal organs requires planning based on diagnostic radiology imaging. The electrode type is selected based on the precise location and measured size of the tumour nodules; for tumours located up to 3 cm (the lower edge of the metastasis) below the surface of the liver, which are more easily accessible to ECT, short-needle electrodes with a fixed hexagonal geometric arrangement are appropriate, while for hard-to-reach and deep-seated metastases, long-needle electrodes with arbitrary geometric arrangement have recently been made available. In line with technological advances and the development of new types of electrodes, experts at the Italian company IGEA designed a new electric pulse generator called the Cliniporator VITAE for treating larger and deep-seated tumours. The generator meets the essential requirements for consumer safety, health and environmental protection as defined by the EU guidelines or regulations, as it has the CE mark.

The distribution of the electrical field within the tissue is an important predictor for the success of ECT tumour treatment, as the change in the transmembrane potential of the cell membrane, which is a prerequisite for successful electroporation, is directly proportional to the strength of the electric field.¹⁹ Numerical modelling is currently the only effective method for predicting the electric field distribution in tissue, as its structure is, by definition, inhomogeneous, nonlinear and in some cases anisotropic. When using long-needle electrodes with an arbitrary geometric arrangement, it is necessary to determine the depth of electrode insertion into the tumour nodule, as well as the

voltage, length and frequency of the supplied electroporation pulses based on numerical modelling in order to achieve the optimal coverage of the tumour nodules with the electric field.⁷

Electroporation Pulse Synchronization Using Electrocardiogram (ECG)

In ECT treatment, the electric current reaches the area around the target due to the high electrical conductivity of the tissue. This increases the likelihood of possible interactions between the electroporation pulses and the heart function when treating deep-seated tumours in internal organs due to the anatomical proximity of the heart. In our clinical study, we will use a synchronization procedure built into the electroporation pulse generator (Cliniporator VITAE) to avoid cardiac dysfunction caused by ECT. So far, this procedure has proven to be effective in preventing cardiac pacing during the 'ventricular sensitivity' period.¹⁴ Nevertheless, further research is urgently needed to verify the effectiveness of the existing synchronization procedure and to determine any short- or long-term effects of electroporation pulses on the heart function.

Preliminary results suggest that ECT does not seriously affect cardiac function though there are statistically significant changes in some parameters of heart rate variability during and after therapy relative to the pre-therapy parameter values.

The analysis of ECG signals recorded during ECT applied to liver tumours shows short-term effects on the cardiac function, even though the delivery of the electroporation pulses was synchronized with the ECG. The effects were expressed as a temporary shortening of the corrected QT interval and an increase in short-term heart rate variability. The analysis of the ECG signals recorded before and after ECT was applied to liver tumours indicates that ECT has longer-term effects on cardiac function, which are expressed as increased heart rate or a shortened RR interval and as reduced long-term heart rate variability parameters (low-frequency component). We find that these changes are most likely at least partly attributable to the effects of analgesics and other medications received by patients in intensive care, as well as to postoperative pain, and not to the effects of the electrochemotherapy itself, although these results have yet to be confirmed. These results could be confirmed by capturing ECG signals before, during and after abdominal surgery, which would include procedures similar to those performed during the ECT of liver tumours. The only difference should be that ECT is not performed during these surgical procedures. The ECG signals captured in this way would serve as a control and would allow these assumptions to be confirmed.

5. Rudolf Z, [name] R, [name] M, Miklavčič D, Vodovnik L, Serša G. Electrochemotherapy with bleomycin. The first clinical experience in malignant melanoma patients. *Radiol Oncol* 1995; 29: 229–35.

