An adverse effect is an undesirable and unexpected sign, symptom or disease, regardless of the cause, that develops or worsens during the study and that includes pathological clinical observations and deviations in the values of laboratory-measured parameters. The latter are only considered a side effect if they require additional treatment or result in the premature withdrawal of the patient from the study.

We will record any side effects that occur during the study and up to 30 days after the end of treatment. If a serious adverse reaction occurs more than 30 days after the end of treatment, the principal investigator will decide whether the complication is study-related or not.

We will record the start and end time of any adverse effect and the cause-and-effect relationship between the adverse effect and the ECT, cancer or other diseases, as well as assessing the severity of the adverse effect and describing the actions that will need to be taken.

The causal relationship between the adverse effect and the ECT will be assessed using the following criteria:

- Not related to the study.
- Probably not related to the study.
- Possibly related to the study.
- Probably related to the study.
- Certainly related to the study.

The severity of the side effects will be assessed using the following grades:

- Grade 1 – mild
- Grade 2 – moderate
- Grade 3 – a difficult complication requiring medical care
- Grade 4 – a life-threatening condition requiring immediate medical assistance
- Grade 5 – death

If a serious adverse effect is recorded during the study, the principal investigator will notify the responsible person at the National Medical Ethics Committee of the Republic of Slovenia in writing within 24 hours. A serious adverse effect is a complication that results in the following:

- death,
- a life-threatening condition requiring immediate medical assistance,
- hospitalization or extended hospitalization,
- the prolonged inability of the patient to perform any task that they were able to perform before the onset of the complication,
- any event or condition that endangers the life or health of the patient and that, according to a medical assessment, could lead to any of the serious complications referred to above.

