7 DATA PROCESSING

The results of the proposed clinical trial will be analysed descriptively by describing the antitumour effect, any adverse effects and the patients' quality of life after treatment of the primary liver tumours.

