8 STATISTICAL ANALYSIS

All data will be entered into a Microsoft Access 2010 database, which will be used for all calculations except for statistical analysis, which will be performed with GraphPad Software (La Jolla, CA, USA). The log-rank (Mantel-Cox) test will be performed on the Kaplan-Meier estimates. A chi-squared test will be used for the statistical comparison of response according to tumor location. A two-tailed P value less than 0.05 will be considered to be statistically significant.

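### The stated aim of proving ECT safe goes beyond what 25 descriptively analysed patients can show: zero serious events would still leave a 95% upper limit of 13.7%

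*Combined protocol and SAP*

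**What the plan says.** The sentence at issue is in Section 2 (Starting Points), at the end of the text on treating primary malignant liver tumours: "The study aims to prove that treating primary liver tumours using ECT is a safe method even in hard-to-reach locations". It is current text and describes this study's own aim.

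The rest of the plan bears on it as follows.

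- **Sample.** Section 1: "In phase I, 10 patients will be included in the study". Section 2: "We aim to include an additional fifteen (15) patients within phase II using this protocol". The total is 25, with no derivation, power or precision target.
- **Purpose elsewhere.** Section 1 speaks of evaluating safety and efficacy. Section 2, shortly before the sentence quoted above, speaks of assessing them.
- **Safety data.** Section 6.3: "We will record any side effects that occur during the study and up to 30 days after the end of treatment". It also grades severity and causality and defines a serious adverse effect. It gives no acceptable rate.
- **Safety analysis.** Section 7 says the results "will be analysed descriptively by describing the antitumour effect, any adverse effects" and quality of life.
- **Inference.** Section 8 has a general rule: "A two-tailed P value less than 0.05 will be considered to be statistically significant". Its chi-squared test compares response between tumour locations. Its log-rank test has no stated endpoint or groups. Neither is assigned to adverse effects.

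**The concern.** Proving safety needs a rate that would count as safe and data able to exclude anything higher. The plan supplies no such rate, and its safety analysis is a description. The part of the aim about hard-to-reach locations has no safety analysis of its own, because the only comparison by location concerns response.

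The risk is that few or no serious events would be read as meeting the aim, although the data would remain compatible with a serious-event rate above one in ten. Section 2 (Clinical Applications of ECT) already reasons this way. It says an earlier study of ECT for liver metastases proves safety and efficacy, mentions the first 17 patients, and reports no serious side effects attributable to ECT. The same section elsewhere says that more work is needed on the ECG synchronization procedure and on cardiac effects, so the document itself treats part of the safety question as open.

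**Working it through.** **Inputs from the documents.** Phase I n = 10 (Section 1). Phase II n = 15 more (Sections 1 and 2). Total 10 + 15 = 25. The plan's sample size cannot be reproduced, because no rate, margin, power or precision is given from which to derive it.

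**Best case: zero patients with a serious event.** The exact (Clopper-Pearson) 95% upper limit for 0 events in n patients is 1 − 0.025^(1/n) two-sided and 1 − 0.05^(1/n) one-sided.

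| n | Two-sided 95% | One-sided 95% |
|---|---|---|
| 10 (phase I) | 1 − 0.025^(1/10) = 30.8% | 1 − 0.05^(1/10) = 25.9% |
| 15 (phase II alone) | 1 − 0.025^(1/15) = 21.8% | 1 − 0.05^(1/15) = 18.1% |
| 25 (all) | 1 − 0.025^(1/25) = 13.7% | 1 − 0.05^(1/25) = 11.3% |

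The Wilson two-sided limits (27.8% for n = 10, 13.3% for n = 25) and the rule of three (3/10 = 30%, 3/25 = 12%) lead to the same conclusion.

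**A few events.** The two-sided exact upper limit for 1/25 is 20.4%. For 2/25 the interval is 1.0% to 26.0%.

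**How often a real risk would go unseen.** The documents give no serious-event rate, so these true rates are assumptions for illustration. P(no events in 25) = (1 − p)^25.

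- p = 5%: 0.95^25 = 28%
- p = 10%: 0.90^25 = 7%

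In phase I alone, a true rate of 10% gives no events with probability 0.90^10 = 35%.

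**Hard-to-reach subset.** Its size is not stated. It cannot exceed 25, and the zero-event limit rises as n falls. If it held 15 patients (an assumption), the two-sided limit would be 21.8%, as in the table.

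**The earlier series.** If the absence of serious attributable events is applied to the 17 patients mentioned, the same method gives 1 − 0.025^(1/17) = 19.5%.

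**The case against.** The strongest reply is that this is one verb in a background section. The formal purpose in Section 1 is to evaluate, Section 2 also says assess, Section 7 promises only description, and Section 8 holds no safety test or decision rule. That is largely right, and it limits the point to wording and a missing interval. It does not remove it. The sentence is the only one that addresses safety in hard-to-reach locations, and the way the earlier series is presented shows how such an aim comes to be declared met.

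A reader might infer more, and the documents do not support it:

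- **That 25 patients is too few.** A sample of this size with descriptive safety reporting is ordinary in a phase I/II study. The mismatch is with the claim.
- **That the study has no comparator.** Section 6.2 plans ECG recordings in 10–15 patients having abdominal surgery without ECT, and Section 2 describes such recordings as a control. They serve the cardiac question only. What is missing is a comparison group for adverse effects in general.
- **That the hard-to-reach group is known to be small.** Section 5 describes the treated patients as having tumours close to the main hepatic veins, and several inclusion criteria select on location, so the group could be nearly the whole sample. Other criteria and the short-needle option may admit easier tumours. The number is unknown.
- **That the analysis plan would itself report proof.** Section 7 commits only to describing. The stronger conclusion would come from the aim in Section 2.

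**Conclusion.** The point holds as a mismatch between one stated aim and the design. With no serious events at all, the study could exclude, at two-sided 95% confidence, only rates above 13.7% in 25 patients or above 30.8% in the 10 phase I patients. On the more lenient one-sided basis the figures are 11.3% and 25.9%, and the conclusion is unchanged. These limits describe what the data could not rule out. They are not estimates of the risk of ECT and do not suggest that it is unsafe.

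The figures assume that all patients are evaluable, that each counts once (at least one serious event or none), that patients are independent, and that the two phases can be pooled for safety. Fewer evaluable patients would widen the limits. The 5% and 10% scenarios are illustrative and are not taken from the documents.

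The change should be made: it affects what the trial may conclude and costs almost nothing.

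**What to change.** 1. **Section 2.** Replace the aim of proving safety with estimation, in line with the purpose in Section 1. For example: *The study aims to estimate the rate of serious adverse effects of ECT for primary liver tumours, overall and in hard-to-reach locations.*
2. **Section 7.** Report the proportion of patients with at least one serious adverse effect, as defined in Section 6.3, with its two-sided exact (Clopper-Pearson) 95% interval. Give it overall and for patients with hard-to-reach tumours. Define that group in advance, for example as patients treated with long-needle electrodes, which Section 2 already links to hard-to-reach and deep-seated lesions.
3. **Section 7.** State that the safety conclusion will be worded by the upper limit of the interval.

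Simple exact intervals should not be extended to response rates by nodule. Section 6.1 classifies response by nodule and the inclusion criteria allow several tumours per patient, so a binomial interval on nodules would be too narrow if responses within a patient are positively correlated. Any response interval should use the patient as the unit or allow for several nodules per patient.

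The cost is a reworded sentence, a few intervals and a less favourable safety claim. No change to sample size, treatment, eligibility or data collection is needed.

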3 PATIENT SELECTION

The suitability of patients for inclusion in the study will be assessed using inclusion and exclusion criteria.

